5. INTRODUCTION

8HA01EXT is an extension study designed to assess the long-term safety and efficacy of recombinant factor VIII fusion protein (rFVIII Fc) in previously treated subjects with hemophilia A. Male subjects of all ages who have completed a preceding study of rFVIII Fc (997HA301, 8HA02PED, or any other rFVIII Fc study) may be eligible for enrollment in this study.

The Note for Guidance on the Clinical Investigation of Recombinant Factor VIII and Human Plasma-derived FVIII Products [CPMP, 2009] was followed in the development of this protocol.

5.1. Profile of Previous Experience

Hemophilia A is an X-chromosome-linked bleeding disorder caused by mutations and/or deletions in the F8 gene resulting in a deficiency of FVIII activity [Mannucci, 2001; Bolton-Maggs and Pasi, 2003]. The coagulation disorder occurs predominantly in males and affects approximately 1 in 10,000 males. The severity of disease is characterized by the endogenous level of FVIII measured in the plasma. Severe hemophilia A is defined as a coagulation activity of FVIII in plasma (FVIII:C) level of <1% (<1 IU/dL). Individuals with severe hemophilia A experience frequent bleeding and recurrent spontaneous bleeding into the soft tissue and joints, leading to joint damage and severe disability. Repeated bleeding into muscles and joints, which often begins in early childhood, results in hemophilic arthropathy and irreversible joint damage. Damage can lead to limited mobility of joints, muscle atrophy, and chronic pain [Rodriguez-Merchan, 2003].

FVIII and factor IX work in concert to activate factor X, a central step in the clotting cascade. The coagulation cascade has 2 pathways, the Contact Activation Pathway (Intrinsic Pathway) and the Tissue Factor Pathway (Extrinsic Pathway). The plasma factors are activated in a cascade one after the other until the soluble plasma protein fibrinogen is transformed into a fibrinous clot.

5.1.1. Therapies for Hemophilia A

There is no cure for hemophilia A, so treatment focuses on the replacement of FVIII with the intravenous (IV) administration of FVIII-containing coagulation products to promote clotting. The goal of treatment with FVIII-containing coagulation products is to raise the circulating level of FVIII to the lowest effective level to achieve either resolution of bleeding (on-demand treatment) or prevention of bleeding (prophylaxis treatment) [WFH, 2005; MASAC, March 2009]. The frequency of administration of FVIII products varies across patients and is tailored to the patient's clinical status, taking into consideration the type of bleeding episode, frequency of bleeding, and goal of treatment for the subject. The dose of FVIII required also varies and has been based on observations over the years and guidelines established by organizations such as the National Hemophilia Foundation of the United States and the World Federation of Hemophilia (WFH [WFH, 2005]).

The use of FVIII-containing plasma-derived coagulation products for people with hemophilia A, available for almost 40 years, has led to vast improvements in quality of life and has increased

CONFIDENTIAL

The information contained herein may not be used, disclosed, or published without the written consent of Biogen Idec MA Inc.

life expectancy. Manufacturing methods for plasma-derived products are now considered to be highly effective in reducing the risk of transmission of enveloped viruses such as HIV and hepatitis B and C. However, these methods may not be effective in reducing the risk of nonenveloped viruses, such as hepatitis A and parvovirus B19. Recombinant coagulation products developed more recently with no animal or human plasma-derived proteins have a safety advantage with a minimal risk of disease transmission [Mannucci, 2001].

Priorities for improving hemophilia A therapy include the development of more convenient dosing options and development of modified FVIII agents with longer half-life ($t_{1/2}$) to decrease injection frequency. Current therapy is focused on home therapies, which, taken prophylactically or administered at the onset of a bleeding episode, reduce short-term disability and long term joint damage and improve patients' quality of life and functional independence [Colvin, 2008].

5.1.2. rFVIII Fc

rFVIII Fc is a novel recombinant Fc fusion protein comprised of a single molecule of B-domain-deleted FVIII attached to the Fc domain of human immunoglobulin G1 (IgG1). This type of construct has been termed a monomeric Fc fusion protein [Dumont 2006]. The Fc enables binding to the neonatal Fc receptor (FcRn), which is responsible for protecting IgG from degradation and confers IgG the 3-week $t_{1/2}$ observed in humans [Ghetie and Ward 2000; Roopenian 2007]. The FcRn is present in humans throughout life and protects IgG from catabolism [Junghans 1996]. rFVIII Fc was designed to offer a longer circulating $t_{1/2}$ than currently available FVIII products, aiming to provide hemophilia A patients with prolonged protection and prophylaxis from bleeding with less frequent dosing.

5.1.3. Summary of Clinical Experience With rFVIII Fc

A completed Phase 1/2a study (998HA101) investigated the safety of a single dose of rFVIII Fc given as an IV injection over 10 minutes to subjects with severe hemophilia A and compared the pharmacokinetics (PK) of rFVIII Fc with Advate[®] (antihemophilic factor [Recombinant], Plasma/Albumin-Free Method, [INN] octocog alfa).

Two dose levels, 25 IU/kg and 65 IU/kg, were evaluated, with 6 subjects receiving Advate 25 IU/kg, and 10 receiving Advate 65 IU/kg. Following a 3-day PK profile for the Advate 25 IU/kg dose group and a 4-day profile for the Advate 65 IU/kg dose group, these subjects then crossed over to receive an equivalent dose of rFVIII Fc. A 7-day PK profile was performed after the 25 IU/kg dose. Following the rFVIII Fc 65 IU/kg dose, subjects underwent a 10-day PK profile. A 28-day safety observation period followed the rFVIII Fc dose, and included inhibitor testing at 14 and 28 days post-dosing.

Safety and tolerability were assessed in all 16 subjects, including FVIII inhibitors and anti-FVIII Fc antibodies, vital signs, hematology, clinical chemistry, and coagulation parameters.

When compared with Advate at both dose levels, rFVIII Fc was well-tolerated. No clinically significant changes in safety parameters occurred and most adverse events (AEs) were mild and resolved without sequelae by the end of the study. No subject developed antibodies or inhibitors during the study period. Compared with Advate, rFVIII Fc demonstrated significantly improved

CONFIDENTIAL

The information contained herein may not be used, disclosed, or published without the written consent of
Biogen Idec MA Inc.

activity, as indicated by longer $t_{1/2}$, increased systemic exposure, and a reduction in clearance, with comparable maximum plasma activity (C_{max}) and recovery. Improved FVIII activity resulted in an increased time to 1% above baseline, approximately 50% to 74% longer at doses of 25 IU/kg and 65 IU/kg, respectively (one-stage aPTT clotting assay); and 51% to 79% longer at 25 IU/kg and 65 IU/kg, respectively (chromogenic assay).

In addition, a Phase 3 study in previously treated subjects age 12 years or older with severe hemophilia A has recently been completed (Study 997HA301). A total of 164 subjects (including 13 subjects aged 12 to 17 years) in the Phase 3 study received at least 1 dose of rFVIII Fc. This included 146 subjects treated for at least 26 weeks and 23 subjects treated for at least 39 weeks, for a total of 102.05 person-years on study.

Compared with Advate, rFVIII Fc demonstrated improved PK activity, as indicated by a 53% longer $t_{1/2}$, a 56% increase in systemic exposure, and a 36% reduction in CL, with comparable C_{max} and recovery (one-stage aPTT clotting assay).

rFVIII Fc was well tolerated in the Phase 3 study. No subject developed an inhibitor to rFVIII Fc. Common AEs observed were consistent with those expected in patients with hemophilia A. Adverse drug reactions were mild and manageable, and the majority were not treatment limiting. One nonserious event of rash required discontinuation of treatment and resolved. There was no Grade 2 or greater allergic reactions or serious vascular thrombotic events. No treatment-related serious adverse events (SAEs) were observed.

Study 8HA02PED (referred to as the pediatric study) is an open-label, multicenter study evaluating the safety, PK, and efficacy of rFVIII Fc in previously treated pediatric patients with severe hemophilia A, who are <12 years of age, and have at least 50 EDs to FVIII products prior to enrollment. Approximately 50 male subjects (25 subjects <6 years of age and 25 subjects 6 to <12 years of age) are planned to complete at least 26 weeks of prophylactic treatment to attain at least 50 EDs. At least 24 of these subjects (12 subjects <6 years of age and 12 subjects 6 to <12 years of age) will undergo an evaluation of the PK profile of pre-study FVIII and rFVIII Fc. Subjects who complete this study will be offered enrollment into the extension trial described in this protocol.

For further details regarding the clinical studies conducted with rFVIII Fc, please refer to the rFVIII Fc Investigator's Brochure.

5.2. Study Rationale

The results of the Phase 1/2a study, the nonclinical data [Dumont, 2009], and the Phase 3 study support further investigation of repeat administration of rFVIII Fc in the prevention and treatment of bleeding episodes in hemophilia A subjects. This extension study will evaluate the long-term safety of rFVIII Fc in subjects with hemophilia A and will allow subjects from the A-LONG (997HA301) pivotal study, the pediatric study (8HA02PED), and other studies to continue treatment with rFVIII Fc.

CONFIDENTIAL

The information contained herein may not be used, disclosed, or published without the written consent of Biogen Idec MA Inc.

5.3. Rationale for Dose and Schedule Selection

Subjects 12 years of age or older will follow either a tailored prophylaxis (individualized), weekly (modified) prophylaxis, personalized prophylaxis, or on-demand (episodic) regimen based on the clinical profile of the subject and by the trough and/or peak (recovery) values, if needed, as observed in the preceding study. Subjects are allowed to change treatment regimens (for example, from prophylaxis to on-demand, or from on-demand to prophylaxis) during the study. Subjects less than 12 years of age will receive 1 of 2 prophylactic regimens, tailored or personalized, and will not have the option to change to a weekly prophylactic or on-demand regimen, unless they reach the age of 12 years during the study, at which time they can use any of the 4 treatment regimens. All treatment regimen changes will be discussed between the Investigator and the subject (and parent/guardian, as applicable). All treatment regimen changes require the approval of the Sponsor Medical Monitor. All regimen changes must occur at a scheduled or unscheduled clinic visit following assessment by the Investigator, and must be documented at that visit. Details (including date of change, new dose and/or dosing interval, and reasons for the change) will be recorded on electronic case report forms (eCRFs).

The starting dose in 8HA01EXT may be based on the subject's results from the preceding rFVIII Fc study. In the completed Phase 3 study, 997HA301, doses between 20 IU/kg and 65 IU/kg were evaluated and shown to successfully maintain a trough level >1% and/or control bleeding. In the pediatric study, 8HA02PED, a regimen consisting of starting doses of 25 IU/kg on Day 1 and 50 IU/kg on Day 4 of rFVIII Fc is used initially. This dosing regimen may be adjusted as indicated by enrollment PK, subsequent FVIII activity trough levels, or bleeding patterns: the dose may be adjusted up to a maximum prophylactic dose of 80 IU/kg and the frequency of administration up to every 2 days, if necessary to maintain adequate FVIII activity trough levels and prevent spontaneous bleeding events.

5.3.1. On-Demand Regimen

The individual dose of rFVIII Fc to treat bleeding episodes will be based on the subject's clinical condition, type and severity of the bleeding event, and if indicated, FVIII levels. A subject's PK profile and dosing levels from the predecessor studies may also be used to guide dosing decisions. Subjects <12 years of age entering from another rFVIII Fc study will not be offered this option, but can receive an on-demand regimen once they reach the age of 12 years during the study.

Please refer to [Appendix A](#) for guidance on dosing decisions.

5.3.2. Prophylaxis Regimens

Details for each dosing option, including, if applicable, date of change, new dose and/or dosing interval, and reason(s) for the regimen change will be recorded on the appropriate eCRF each time a change is made.

5.3.2.1. Option 1: Tailored Prophylaxis

The Investigator may consider the following options for tailored prophylaxis to target a FVIII trough of up to 5%, but is encouraged to use the lowest effective dose targeting a FVIII trough

CONFIDENTIAL

The information contained herein may not be used, disclosed, or published without the written consent of Biogen Idec MA Inc.

level between 1% and 3%. If bleeding episodes occur at FVIII trough levels of 1% to 3%, further adjustments to dose or interval over the course of the study will target trough levels of up to 5%.

Dosing is approximately 25 IU/kg to 65 IU/kg every 3 to 5 days, or dosing 2 times per week at approximately 20 IU/kg to 65 IU/kg on Day 1 and 40 IU/kg to 65 IU/kg on Day 4. The dose and interval should be based on the subject's clinical profile observed in the preceding rFVIII Fc study, and/or his individual PK (if available), and FVIII trough and/or peak (recovery) values. In pediatric subjects, doses may be adjusted up to a maximum prophylactic dose of 80 IU/kg and the interval decreased to every 2 days, if necessary to maintain adequate FVIII activity trough levels and prevent spontaneous bleeding events.

5.3.2.2. Option 2: Weekly Prophylaxis

Dosing is approximately 65 IU/kg at weekly intervals. The dose should be based on the subject's clinical profile observed in the preceding rFVIII Fc study, and/or his individual PK (if available), and FVIII trough and/or peak (recovery) values. Subjects <12 years of age entering from another rFVIII Fc study will not be offered this option, but can receive a weekly prophylaxis regimen once they reach the age of 12 years during the study.

5.3.2.3. Option 3: Personalized Prophylaxis

If optimal prophylaxis dosing cannot be achieved using either of the above options, the Investigator may further personalize dosing to meet the needs of individual subjects.

The Investigator may consider the following personalized dosing options:

- Addition of "prevention" doses prior to strenuous activity.
- Targeting a FVIII trough level of >3%, if the bleeding history and/or activity level requires.
- Dosing less frequently.

The Investigator is not limited to the options above, and should consult the Medical Monitor for further consideration of a subject's dosing options. The personalized prophylaxis dosing option will require consultation with the Medical Monitor.

5.3.3. Surgery and Rehabilitation

If a subject requires emergent or elective surgery while participating in this study, he may be treated with the dose and regimen of rFVIII Fc deemed appropriate for the type of surgery. All major surgeries will be reported as SAEs.

All major surgical procedures must take place in a center that can provide study treatment, trained study personnel, post-operative assessments, and hematological consultation by the Investigator or Co-Investigator. If the surgery does not occur in such a setting, the subject will be withdrawn from the study. See Section 10.1.3 for provisions when a subject requires major surgery.

CONFIDENTIAL

The information contained herein may not be used, disclosed, or published without the written consent of Biogen Idec MA Inc.

If surgery-related dosing is continued during post-operative rehabilitation and/or physical therapy, the dose of rFVIII Fc will be adjusted to achieve a FVIII trough at a sufficient level to maintain hemostasis.

Subjects will return to a regular rFVIII Fc regimen once all dosing for the post-operative rehabilitation period has been completed. For subjects undergoing major surgery, a visit is required 1-2 weeks after surgery (Visit 3, not required for minor surgery). Visit 4 (Last Post-Operative Visit, not required for minor surgery) occurs when the subject returns to a regular rFVIII Fc regimen as determined by the Investigator, and is required only if the subject did not return to a regular rFVIII Fc regimen at Visit 3.

The surgical period will begin with the subject's first dose of rFVIII Fc given for the surgery (i.e., the pre-surgery dose). This is the pre-operative period of the surgery. The intra-operative period is defined as the time the surgery begins to the time the surgery completes. The post-operative care period is defined as the time period following the completion of the surgery through the last dose of rFVIII Fc given for the surgery, as judged by the Investigator/Surgeon, including doses given to prevent bleeding during the post-operative rehabilitation period.

For subjects from the pediatric study (8HA02PED) who undergo major surgery and enter the extension study before completing their Last Post-Operative Visit from the prior rFVIII Fc study, an unscheduled visit may be conducted to perform the Last Post-Operative Visit assessments when the subjects switch from their post-surgery dosing regimen to a regular rFVIII Fc regimen (as outlined in Sections 5.3.1 and 5.3.2). The following assessments must be performed at that time:

- Physical examination
- Weight
- Hematology
- Subject's assessment of response
- FVIII activity (to be measured at trough immediately prior to the injection and at peak [recovery] 30 [±3] minutes from the start of injection)
- Subject eDiary review
- Nijmegen-modified Bethesda assay (inhibitor assay)
- rFVIII Fc administration and accountability
- AE/SAE monitoring and recording
- Concomitant therapy/procedures recording

5.4. Potential Risks and Benefits

Please refer to the current Investigator's Brochure for descriptions of the potential risks and benefits of rFVIII Fc.

CONFIDENTIAL

The information contained herein may not be used, disclosed, or published without the written consent of Biogen Idec MA Inc.

6. STUDY OBJECTIVES AND ENDPOINTS

6.1. Objectives

6.1.1. Primary Objective

The primary objective of the study is to evaluate the long-term safety of rFVIII Fc in subjects with hemophilia A.

6.1.2. Secondary Objectives

The secondary objective of the study is to evaluate the efficacy of rFVIII Fc in the prevention and treatment of bleeding episodes in subjects with hemophilia A.

6.2. Endpoints

6.2.1. Primary Endpoint

The primary endpoint is the occurrence of inhibitor development

6.2.2. Secondary Endpoints

The secondary endpoints are as follows:

- The annualized number of bleeding episodes (spontaneous and traumatic) per subject
- The annualized number of spontaneous joint bleeding episodes per subject
- The total number of days of exposure per subject per year
- The consumption of rFVIII Fc as total dose per kg per subject per year
- Physician's global assessment of the subject's response to his treatment regimen using a 4-point scale
- Subject's assessment of response to the treatment of bleeding episodes using a 4-point scale

6.2.3. Major Surgery Endpoints

The major surgery endpoints are as follows:

- Investigator/Surgeon assessment of hemostatic response to surgery using the 4-point bleeding response scale
- Number of injections and dose per injection to maintain hemostasis during the surgical period.
- Estimated blood loss (mL) during surgery and post-operative period
- Number of blood product units transfused during surgery

CONFIDENTIAL

The information contained herein may not be used, disclosed, or published without the written consent of Biogen Idec MA Inc.

6.2.4. Patient-Reported Outcome Endpoints

The following patient-reported outcomes will be assessed. Subjects will only take the questionnaires that they completed during the parent study. If a subject goes outside of the age range for a questionnaire, they should no longer complete the questionnaire. The Investigator will administer the age-appropriate questionnaire at the appropriate visits.

Quality of Life (QoL) questionnaires:

- Haem-A-QoL
- Haemo-QoL
- Hemo-Sat-Patient Satisfaction Scale for parents/guardians, Version 15
- Canadian Hemophilia Outcomes-Kids' Life Assessment Tool (CHO-KLAT)
 - Children, Version 2.0 (for children previously enrolled in study 8HA02PED who are less than 18 years of age).
 - Proxy, Version 2.0p (for parents/guardians of children previously enrolled in study 8HA02PED and who are less than 18 years of age)
- EQ-5D Y
- EQ-5D-3L

Health outcomes related to hemophilia will include:

- Number of hospitalizations excluding planned hospitalizations, elective surgery documented at Visit 1, and emergent surgery
- Number of emergency room visits
- Number of physician visits, excluding study visits
- Number of hospitalization days
- Number of days off work, school, day care, or preschool
- Number of days off work for the parent or caregiver

CONFIDENTIAL

The information contained herein may not be used, disclosed, or published without the written consent of Biogen Idec MA Inc.

7. STUDY DESIGN

7.1. Study Overview

This is an open-label, multi-center, long-term study of IV administration of rFVIII Fc in previously treated patients (PTPs) with hemophilia A who have completed the A-LONG study (997HA301), the pediatric study (8HA02PED), or any other study with rFVIII Fc. This is a global study and will be offered to those countries participating in these studies.

Based on estimated sample sizes from these studies, approximately 194 subjects from the ongoing A-LONG study and the pediatric study may be eligible to enroll in this extension study. The End of Treatment (EOT) Visit of the previous study may serve as the initial visit of the extension study. Assessments performed at this visit will be used to confirm eligibility for participation in the extension study.

Study visits are scheduled at 6-month (± 2 weeks) intervals following completion of Visit 1. Unscheduled visits may occur as deemed necessary by the Investigator. For subjects who enter the extension study and undergo surgery before completing their Last Post-Operative Visit from the prior rFVIII Fc study, the Last Post-Operative Visit assessments will be performed when the subjects switch from their post-surgery dosing regimen to a regimen outlined in Section 5.3 (see Section 5.3.3 for list of assessments). For subjects who have fewer than 50 exposure days (EDs) with rFVIII Fc following completion of Visit 1, a visit may be conducted to perform inhibitor testing at the time subjects reach 10-15 EDs, 50-75 EDs, and 100-125 EDs, as applicable. If the timing does not coincide with a scheduled visit, an unscheduled visit may be conducted.

For subjects undergoing surgery, post-operative clinic visits may be more frequent. For subjects undergoing major surgery, a visit is required 1-2 weeks after surgery (Visit 3, not required for minor surgery). Visit 4 is required only if subjects who had major surgery did not return to a regular rFVIII Fc regimen as determined by the Investigator at Visit 3. All major surgeries will be reported as SAEs. Scheduled visits will include safety and efficacy assessments, and FVIII activity measurements to assess trough and peak (recovery) (Section 4). In addition, the site will continue to contact study subjects and/or caregivers by telephone on a bimonthly basis to review AEs, treatment compliance, and use of concomitant medications and therapies.

Treatment will be administered as tailored prophylaxis, weekly prophylaxis, personalized prophylaxis, or as an on-demand regimen. Subjects 12 years of age or older will be able to switch from one regimen to another at scheduled or unscheduled visits during the study, per Investigator discretion. Subjects less than 12 years of age will receive 1 of 2 prophylactic regimens, tailored or personalized, and will not have the option to change to a weekly prophylactic or on-demand regimen, unless they reach the age of 12 years during the study, at which time they can use any of the 4 treatment regimens.

To ensure accuracy of FVIII trough/peak (recovery) and inhibitor testing, subjects following a prophylaxis regimen should schedule clinic visits 48 hours after the previous dose of rFVIII Fc, whenever possible.

CONFIDENTIAL

The information contained herein may not be used, disclosed, or published without the written consent of Biogen Idec MA Inc.

Subjects first dosed with rFVIII Fc when <12 years of age will be followed to at least 100 EDs, even if rFVIII Fc becomes commercially available.

All subjects will have the opportunity to continue in this study for up to 4 years or until rFVIII Fc is commercially available in the applicable participating country.

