6. To be performed at the central laboratory. FVIII activity is determined by one-stage aPTT clotting assay and two-stage chromogenic assay performed at the central laboratory. For FVIII inhibitor and rFVIIIIFc antibody testing, a wash out of at least 48 hours is recommended. For subjects who have fewer than 50 exposure days (EDs) with rFVIIIIFc following completion of Visit 1, a visit may be conducted to perform inhibitor testing at the time subjects reach 10 to 15 EDs, 50 to 75 EDs, and 100 to 125 EDs, as applicable. If the timing does not coincide with a scheduled visit, an unscheduled visit may be conducted. A portion of the blood sample collected will be stored for future anti-rFVIIIIFc antibody testing. Samples will be archived for testing (if required) for immunology or further coagulation assays, or for clarification of any clinical or laboratory AE. Inhibitor and rFVIIIIFc antibody testing should also be done when deemed clinically relevant.
7. Hematology includes: white blood cell count (WBC), differential, platelet count, hemoglobin, hematocrit.
8. Blood chemistry includes: electrolytes (sodium, potassium, chloride), glucose, total protein, total bilirubin, alanine aminotransferase (ALT), aspartate aminotransferase (AST), alkaline phosphatase (ALP), blood urea nitrogen (BUN), and serum creatinine.
9. Tailored prophylaxis, weekly prophylaxis, and personalized prophylaxis regimens: FVIII activity to be measured at trough immediately prior to the injection, and at peak (recovery) 30 (\pm 3) minutes from the start of injection. On-demand regimen: FVIII activity to be measured at the discretion of the Investigator.
10. The sample for DNA-based testing is optional and may be collected at any time during the study, not exclusively at Visit 1.

CONFIDENTIAL

The information contained herein may not be used, disclosed, or published without the written consent of Biogen Idec MA Inc.

11. Patient-reported outcomes should be completed only if they were conducted during the parent study: Questionnaires to be completed every 6 months at scheduled clinic visits. Questionnaires will be provided under separate cover.
12. Changes in patient-reported health outcomes conducted during the parent study to be queried in the subject's electronic patient diary (eDiary) on an ongoing basis, and details to be recorded in the electronic case report form (eCRF).

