3. To be performed at the central laboratory. Hematology includes: WBC, differential, platelet count, hemoglobin, and hematocrit. Blood chemistry includes: electrolytes (sodium, potassium, and chloride), glucose, total protein, total bilirubin, ALT, AST, ALP, BUN, and serum creatinine.
4. Subjects who require post-operative rFVIIIIFc treatment for a bleeding episode at home will record their assessment of response to treatment in the eDiary; this assessment is to be made approximately 8 to 12 hours from the time the rFVIIIIFc injection was given to treat the bleeding episode and prior to any additional doses of rFVIIIIFc given for the same bleeding episode.
5. The Investigator/Surgeon will record the assessment of the subject's response to treatment during surgery using a 4-point scale. This assessment will be done within 24 hours after surgery. See [Appendix C](#) and [Appendix E](#).
6. FVIII activity levels should be measured prior to the pre-operative (loading) dose of rFVIIIIFc, and at 30 ± 5 minutes post-dosing. A repeat sample will be taken approximately 6 to 9 hours after this dose, but may alternatively follow the local standard of care for determination of subsequent rFVIIIIFc dosing. During the subject's hospitalization, FVIII activity will be measured daily at the local laboratory, and a plasma aliquot will be prepared for each blood sample drawn for subsequent analysis at the central laboratory.
7. Inhibitor and anti-rFVIIIIFc antibody testing to be performed 2 to 4 weeks prior to surgery, pre-operatively on the day of surgery, 1-2 weeks after surgery, and at the last post-operative visit (for minor surgery, testing is not performed at the last 2 timepoints). For FVIII inhibitor and antibody testing, a wash out of at least 48 hours is recommended.
8. Visit 3 (1-2 Weeks Post Surgery) and Visit 4 (Last Post-Operative Visit) are not performed for subjects who undergo minor surgery. For major surgery, Visit 4 occurs when the subject returns to a regular rFVIIIIFc regimen as determined by the Investigator, and is not required if the return to a regular rFVIIIIFc regimen occurs at Visit 3.

CONFIDENTIAL

The information contained herein may not be used, disclosed, or published without the written consent of Biogen Idec MA Inc.

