7.1.2. Inhibitor Testing

If inhibitor development is suspected at any time during the study (for example, the expected plasma FVIII activity levels are not attained, or if bleeding is not controlled as expected following dosing), inhibitor testing will be performed by the central laboratory. The definition of a positive result for inhibitor is any inhibitor (≥ 0.6 BU/mL) identified and confirmed on 2 separate samples drawn approximately 2 to 4 weeks apart. Both tests must be performed by the central laboratory using the Nijmegen-modified Bethesda assay.

A high-titer inhibitor is defined as ≥ 5.00 BU/mL identified and confirmed on 2 separate samples drawn approximately 2 to 4 weeks apart. Both tests must be performed by the central laboratory using the Nijmegen-modified Bethesda assay.

When an inhibitor test is performed at the local laboratory, an aliquot of the sample must be sent in parallel to the central laboratory.

For FVIII inhibitor testing, a wash out of at least 48 hours is recommended.

For subjects who have fewer than 50 exposure days (EDs) with rFVIII Fc following completion of Visit 1, a visit may be conducted to perform inhibitor testing at the time subjects reach 10-15 EDs, 50-75 EDs, and 100-125 EDs, as applicable. If the timing does not coincide with a scheduled visit, an unscheduled visit may be conducted.

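### Prophylaxis visits are timed 48 hours after the last dose to measure trough, but at 3- to 5-day or weekly intervals a sample then overstates the trough

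*Protocol*

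**What the plan says.** Section 7.1 of the protocol introduces the visit timing with its purpose, "To ensure accuracy of FVIII trough/peak (recovery) and inhibitor testing", and then states that "subjects following a prophylaxis regimen should schedule clinic visits 48 hours after the previous dose of rFVIII Fc, whenever possible". It does not distinguish between regimens, and it gives 48 hours as a time, not as a minimum.

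Footnote 9 to the Screening and Treatment Period schedule tells sites when to sample in all three prophylaxis regimens: "FVIII activity to be measured at trough immediately prior to the injection", with the peak about 30 minutes from the start of that injection.

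Elsewhere 48 hours is a lower bound and concerns inhibitor or antibody sampling only. Section 7.1.2 says "For FVIII inhibitor testing, a wash out of at least 48 hours is recommended". Footnote 7 to the Surgery Visits schedule says "For FVIII inhibitor and antibody testing, a wash out of at least 48 hours is recommended", and footnote 6 to the main schedule is to the same effect.

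The dosing intervals are longer than 48 hours in the standard regimens:

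- Tailored (Section 5.3.2.1): "Dosing is approximately 25 IU/kg to 65 IU/kg every 3 to 5 days", or twice weekly on Days 1 and 4.
- Weekly (Section 5.3.2.2): "Dosing is approximately 65 IU/kg at weekly intervals".
- Every 2 days is named only as an adjustment for paediatric subjects, although personalized prophylaxis (Section 5.3.2.3) does not rule it out.

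Trough targets are 1-3% for tailored prophylaxis, rising to at most 5% if bleeds occur at that level. One personalized option is "Targeting a FVIII trough level of >3%, if the bleeding history and/or activity level requires".

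**The concern.** A site that follows both Section 7.1 and footnote 9 brings the subject in at 48 hours, draws the sample, injects, and records the value as trough. For a subject on a 3-, 4-, 5- or 7-day interval, that is a mid-interval level.

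What is at stake is dosing guidance. The Investigator is encouraged to use the lowest effective dose that gives a 1-3% trough, so a reading above that range can be taken as adequate or as room to reduce. The step up towards 5% in Section 5.3.2.1 is written for bleeds that occur at troughs of 1-3%; a bleeding subject whose true trough is in that range could read above it and seem not to qualify. Under Section 7.1.4.2, contact with the Sponsor after a single spontaneous bleed depends on the Investigator's concern that the trough is too low, so that safeguard leans partly on the same measurement.

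**Working it through.** **Direction.** While activity is falling, any sample taken before the end of the interval exceeds the end-of-interval level. SAP Section 5.1.1 supports continued decline after 48 hours: for most subjects activity is below 1% after 7 days (studies in patients 12 or older) or 4 days (paediatric study). The gaps are 72-120 h (every 3 to 5 days), 72 h and 96 h (Days 1 and 4) and 168 h (weekly). Only a 48-h interval gives no overstatement.

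**Size.** The documents give no half-life in hours and no recovery figure, so this part is illustrative.

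- From the protocol: doses of 25-65 IU/kg, targets of 1% and 3%, and the intervals T above.
- Assumed: mono-exponential decline and recovery of 1.5-2.5 IU/dL per IU/kg.
- Peak P = dose x recovery, so P runs from 25 x 1.5 = 37.5 to 65 x 2.5 = 162.5.
- With activity(t) = P x 2^(-t/h) and a true trough L at time T, the half-life is h = T / log2(P/L), and the 48-h reading is L x (P/L)^(1 - 48/T).

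Example, T = 72 h and L = 1%: 37.5^(1/3) = 3.35% and 162.5^(1/3) = 5.46%.

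| Interval | 48-h reading, true trough 1% | Implied half-life | 48-h reading, true trough 3% | Implied half-life |
|---|---|---|---|---|
| 72 h | 3.35-5.46% | 13.8-9.8 h | 6.96-11.35% | 19.8-12.5 h |
| 96 h | 6.12-12.75% | 18.4-13.1 h | 10.6-22.1% | 26.3-16.7 h |
| 120 h | 8.80-21.2% | 22.9-16.3 h | 13.7-32.9% | 32.9-20.8 h |

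For weekly 65 IU/kg (P = 97.5 to 162.5, T = 168 h), a true 1% trough reads 26.4-38.0%; that regimen has no stated trough target.

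**Sensitivity to the decline model.** If the terminal phase starts at half the peak, the true-1% readings become 2.66-4.33% (72 h), 4.33-9.01% (96 h) and 5.80-14.0% (120 h). The lowest of these falls inside the 1-3% target; the others do not.

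**Cross-check by another route.** The ratio of the 48-h level to the level at T is 2^((T - 48)/h), whatever the dose. For an assumed half-life of 24 h down to 12 h this is 2 to 4 at 72 h, 4 to 16 at 96 h and 8 to 64 at 120 h. Read backwards, a 48-h value of 5% means a true trough of 2.5-1.25% at 72 h, 1.25-0.31% at 96 h and 0.62-0.08% at 120 h.

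**Can a reading inside the target hide a trough below 1%?** A 48-h reading of 3% needs h = 48 / log2(P/3), which is 13.2 h at P = 37.5 and 8.3 h at P = 162.5. A reading of 3% or less therefore needs a half-life of about 13 h or less, so this happens mainly in fast clearers.

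**The case against.** The strongest reply is that the sampling instruction itself is right. Footnote 9 asks for a trough immediately before the injection, and a subject dosed every 4, 5 or 7 days has no prophylactic injection due at 48 hours. Following Section 7.1 literally would mean injecting early, outside the ±24-hour interval-compliance window in SAP Section 6.5.5.2 for all but the 3-day interval. That suggests an inhibitor wash-out minimum carried into an overview sentence without its qualifier. This is probably how the sentence arose, but it does not cure it: the footnote's word moves no visit, and the only scheduling instruction found says 48 hours.

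Several further points stand and limit the weight:

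- The advice is soft, and how sites actually sampled is not known. The Laboratory Manuals (Section 19.1.4) may say more; they are not available, so they cannot be counted as a correction.
- Inhibitor testing, which feeds the primary endpoint, is also a stated purpose, and 48 hours meets its minimum.
- Clinical profile, individual PK and peak also inform dosing. Repeated bleeds allow dose review (Section 7.1.4.3), regimen changes need Medical Monitor approval (Section 5.3), and staff review diary doses (Section 10.4). These limit the harm but leave the reading wrong.
- The illustration omits the 20 IU/kg Day 1 dose and the 80 IU/kg paediatric maximum. Including them changes little. At P = 20 x 1.5 = 30, a true 1% trough at 72 h reads 30^(1/3) = 3.1%, and the half-life threshold above becomes 48 / log2(30/3) = 14.4 h. At P = 80 x 2.5 = 200, the 72-h reading is 200^(1/3) = 5.8%.

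**Conclusion.** The concern holds. Section 7.1 sets one visit time for every prophylaxis subject, partly for the sake of trough accuracy, and that time is wrong for trough at any interval longer than 48 hours. The upward direction needs only that activity is still falling. The size rests on assumed recovery and mono-exponential decline. Under those assumptions, a tailored-prophylaxis subject whose true trough lies in the 1-3% target would read above it.

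The importance is minor to moderate. The SAP only lists FVIII activity (Section 7.7), the inhibitor endpoint is untouched, and nothing in the documents shows that an overstated reading led to under-dosing. It is still worth correcting, because the instruction gives a misleading value for a quantity used to choose dose and interval.

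**What to change.** Reword the sentence in Section 7.1 so that prophylaxis visits fall just before the subject's next due prophylactic dose and no sooner than 48 hours after the previous one. This satisfies footnote 9 and the inhibitor wash-out together for any interval of 48 hours or more. No dose or trough target needs to change.

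Optionally, show hours since the last dose in the FVIII activity listing, so that recorded troughs can be interpreted, including those from visits already held. The SAP already plans a listing of all injections, so the value should be derivable.

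The cost is one sentence in the protocol or a site memo, and visits that are slightly harder to schedule.
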